Hazardous alcohol use is prevalent among PrEP users in Canada,¹⁰ which in turn has the potential to contribute to suboptimal PrEP adherence, poor retention in PrEP care, and condomless sex/STIs while on PrEP (e.g.,¹¹⁻¹⁷). The impact of alcohol on these PrEP-related behaviours may also become exacerbated in the presence of concurrent issues such as substance use and depression, thus reflecting a potential syndemic effect (i.e., the combined presence of

multiple issues leads to a greater detrimental impact).¹⁸ Substance use and depression frequently co-occur with alcohol consumption among MSM populations.¹⁹ Addressing hazardous alcohol use and concurrent conditions in PrEP-prescribed hazardous MSM-drinkers is therefore crucial for maximizing the HIV-preventive benefits of PrEP treatment.

II. Rationale and Study Objectives

This investigation follows a syndemic approach and seeks to explore whether a brief, stand-alone, alcohol-reduction intervention (with modules on substance use and depression) would be feasible, acceptable, and potentially efficacious within the context of PrEP treatment. The impact of traditional alcohol-reduction interventions on HIV-related outcomes has been variable, potentially because other concurrent conditions that can adversely impact health outcomes may have remained unaddressed. Our proposed intervention will distinctly target alcohol consumption and address key concurrent conditions among hazardous drinking, PrEP-prescribed MSM; thereby attending to, and accounting for, the potential synergistic detrimental impact that these concurrent conditions may have on PrEP-related behaviors. As there is a high prevalence of these concurrent conditions among MSM populations, the comprehensiveness and uniqueness of our intervention will be particularly well-suited for MSM who rely on PrEP as an HIV risk-reduction strategy.

Findings from this research will have the potential to guide future initiatives to address hazardous alcohol use and concurrent conditions within the context of PrEP treatment. Improving PrEP treatment outcomes could ultimately help reduce the likelihood of HIV acquisition among this population.

III. Specific Aims

The specific aims of this study are to:

[figure not shown]
- 1) Assess the feasibility and acceptability of implementing an alcohol-focused brief intervention with a sample of hazardous drinking, PrEP-prescribed MSM.

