Alcohol consumption. Behavioral measures and a biomarker test will be employed to evaluate **Specific Aim 2**. The AUDIT,²⁰ included as part of the pre-screening process at baseline, will be incorporated into 3-month and 6-month follow-up assessments to identify changes in hazardous drinking over time. Two supplemental self-report alcohol items will be included in all assessments to measure 1) the number of drinks consumed in a typical week, and 2) the highest number of drinks consumed on a single occasion.²⁹ As an objective measure of alcohol use, an alcohol derivative, phosphatidylethanol (PEth), will be assessed from dried blood spots (DBS) obtained at baseline, 3-months, and 6-months. PEth has been shown to be highly correlated with several measures of alcohol consumption;³⁰ it has been used as a clinical marker for chronic excessive drinking and binge drinking;³⁰⁻³⁴ and has been employed as a primary outcome in alcohol treatment trials.^{35,36} The half-life of PEth has an estimated range of 4-12 days, and it has demonstrated a high degree of sensitivity (i.e., >95%) and specificity (i.e., 100%) when comparing patients presenting for alcohol treatment to those who abstain or only consume alcohol at low levels.³⁷⁻⁴¹ PEth levels will be measured using liquid chromatography-tandem mass spectrometry, and values will be examined based on a dichotomy using a cut-off of ≥ 35 ng/ml to identify hazardous drinking.⁴²

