Substance use and Depression. Substance use other than alcohol will be assessed using the National Institute on Drug Abuse (NIDA) - Modified Assist Screening Tool (NIDA M-ASSIST).⁵⁷ This measure queries lifetime use of a variety of substances, frequency of substance use during the past three months, and negative consequences experienced as a result of substance use. Participants will be identified as possessing a potential substance use issue based on NIDA M-ASSIST scoring. Participants will complete the Center for Epidemiologic Studies Depression Scale-10 (CESD-10).⁵⁸ A score ≥ 10 will be used as an indicator of the presence of marked depressive symptomatology.⁵⁸ Both measures will be administered at baseline and at the two follow-up time points.

It should be noted that the demographic and behavioral measures (i.e. alcohol consumption, PrEP adherence, retention in care and engagement in condomless sex) included in this study were previously approved in the first phase of this study (CAMH REB# 101/2017-02; UHN REB# 18-5014).

Data Analysis

Statistical power. As this is a feasibility study and not intended as a definitive clinical trial, sample size considerations focus on expected effect sizes detectable with the design. The following effect size for the variable that likely has the least power (i.e., adherence –**Aim 3**) can be detected based on the following assumptions: there is a combined effect of 1) the suggested alcohol intervention on alcohol intake,⁵⁹ and 2) the effect of lowered alcohol intake on PrEP adherence.¹¹ Suboptimal PrEP adherence, defined as taking $<80\%$ of all doses, was estimated based on the literature¹¹ and assumed to be 30% among heavy alcohol users.⁸ With the current sample size, we would be able to significantly detect Odds Ratios of 3 and higher, and assuming confounding with an R^2 of other variables on the dependent variable, Odds Ratios of 3.5 and higher. We will be able to detect differences in proportions of about 20% with a 95% Confidence Interval between 2% and 28%.⁶⁰ Other factors in **Aims 2, 3, and 4** can detect smaller effect sizes.

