Statistical analyses. Analyses pertaining to feasibility and acceptability indicators (**Aim 1**) will be based on descriptive statistics involving frequency counts (e.g., intervention completion rates) and mean scores (i.e., acceptability measure). The anticipated patterns pertaining to **Aims 2, 3, and 4** will be tested with generalized linear mixed effect models including random intercepts for every patient,^{61,62} based on the expectation that the intervention group will have better outcomes at both follow-up time points. Mixed effect models have fewer assumptions compared to more

traditional repeated measures of analyses of variance⁶¹ with respect to missing values.^{63,64}

For the quantification of the causal impact of alcohol, we will additionally use path models, where alcohol consumption levels will be introduced into the equations, with the hypothesis that the introduction of this variable will make the differences between experimental and control groups disappear.

Reference List

1. Public Health Agency of Canada. (2015) HIV and AIDS in Canada: Surveillance Report to December 31, 2014. Ottawa: Minister of Public Works and Government Services Canada. Available at: <http://www.phac-aspc.gc.ca/aids-sida/publication/epi/2010/index-eng.php>. Accessed April 13 2017.
2. Public Health Agency of Canada. (2015) Summary: Estimates of HIV Incidence, Prevalence and Proportion Undiagnosed in Canada, 2014. Available at: <http://healthycanadians.gc.ca/publications/diseases-conditions-maladies-affections/hiv-aids-estimates-2014-vih-sida-estimations/index-eng.php>. Accessed April 13 2017.

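### The path analysis would judge alcohol's causal role by whether the arm difference vanishes, without estimating an indirect effect or adjusting for depression and substance use

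*Combined protocol and SAP*

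**What the plan says.** The main analysis of Aims 2 to 4 is a set of mixed models comparing the arms. After it, the Statistical analyses paragraph continues: "For the quantification of the causal impact of alcohol, we will additionally use path models". Alcohol consumption is to enter the equations, "with the hypothesis that the introduction of this variable will make the differences between experimental and control groups disappear". That sentence is the whole specification. It gives no indirect effect, interval, decision rule or covariates.

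Other sections bear on it:

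- The background says "Substance use and depression frequently co-occur with alcohol consumption among MSM populations". The Rationale refers to "the potential synergistic detrimental impact that these concurrent conditions may have on PrEP-related behaviors".
- CESD-10 and NIDA M-ASSIST are both available: "Both measures will be administered at baseline and at the two follow-up time points" (Additional Measures). Neither is assigned to the path models.
- The Statistical power paragraph builds the expected adherence effect from the intervention's effect on drinking and "the effect of lowered alcohol intake on PrEP adherence". Mediation through alcohol is therefore the plan's own working model.
- The Intervention section appends a resource module on substance use and depression for participants whose survey answers suggest a problem. TAU receives nothing.

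**The concern.** There are two separate difficulties.

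First, an arm difference can be absent after alcohol is added because alcohol carries the whole effect, because there was never an effect, or because the trial is too small to see a direct one. A hypothesis stated only as the difference vanishing does not separate these. It also gives no estimate of how much of the effect runs through alcohol, although quantification is the stated purpose.

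Second, randomisation protects the path from arm to alcohol but not the path from alcohol to outcome. The protocol itself says depression and substance use go along with drinking and may worsen PrEP behaviours. If they drive both, an unadjusted alcohol path can credit alcohol with their effect. What is at stake is the causal statement about alcohol that the pilot would pass on to later work.

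**Working it through.** The documents give no figure for the path analysis, so there is none to reproduce.

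**Inputs from the protocol.** 120 participants at 2:1, so 80 intervention and 40 TAU. Suboptimal adherence is 30% among heavy drinkers (Statistical power). The protocol assigns that rate to no arm; I assume TAU.

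**Assumed inputs.** Two-sided 5% tests; a single follow-up visit with complete data; alcohol scaled to SD 1; an intervention shift in alcohol of 0.2 to 0.5 SD; alcohol-outcome OR of 2 to 3 per SD under full mediation. A strong common cause has correlation 0.5 with alcohol and log-OR 0.8 on the outcome; a weaker one has 0.3 and 0.5.

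**Step 1. Arm term non-significant after adding alcohol.**

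- No effect: the true arm coefficient is 0, so P = 1 − 0.05 = 0.95. Simulated: about 95%.
- Full mediation: the true arm coefficient given alcohol is also 0, so P is again 0.95. Simulated: about 95%.
- Wholly direct effect: P is roughly 1 − power of the arm comparison. At OR 1/3 the TAU odds 0.30/0.70 = 0.429 become 0.143, a rate of 0.143/1.143 = 12.5%. Power at 40 versus 80 is 63.5%, so P is about 1 − 0.635 = 0.365. Simulated: about 40% (repeat runs 37-40%). At OR 1/2, simulated: about 66% (repeat runs 66-69%).

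The first two situations cannot be told apart by this rule. The third differs from them, but only by as much as the trial has power for a direct effect.

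**Step 2. False mediation when alcohol has no effect on the outcome.** The test requires both paths (arm to alcohol, alcohol to outcome) to be significant.

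- Arm to alcohol: SE = √(1/80 + 1/40) = 0.194. Power is Φ(0.5/0.194 − 1.96) = 0.73 at 0.5 SD and Φ(0.3/0.194 − 1.96) = 0.34 at 0.3 SD.
- With a valid alcohol-to-outcome test, the false-positive rate is about 0.73 × 0.05 = 3.7% and 0.34 × 0.05 = 1.7%.

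| Alcohol shift | Strong common cause, unadjusted | Weaker common cause, unadjusted | Adjusted for the common cause |
|---|---|---|---|
| 0.3 SD | about 14% | about 4% | about 2% |
| 0.5 SD | about 29% | about 8% | about 4% |

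The adjusted column agrees with the hand calculation. The excess in the unadjusted columns is confounding of the alcohol path.

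**Step 3. Power of the replacement.** At a 0.2 SD shift the arm-to-alcohol path has power of about Φ(0.2/0.194 − 1.96) = 0.18. At OR 2 per SD the alcohol-to-outcome path is significant in 88.6% of trials. The product is 0.18 × 0.886 = 0.16; simulated about 15%, before any loss from covariates.

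**The case against.** The strongest reply is that the protocol states a hypothesis, not a significance rule, and that path models ordinarily yield an indirect effect. This stands in part. The rule in Step 1 is my reading, and the 95% figures describe that reading only. But the text commits to no estimate or interval, so the gap remains.

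A reader might infer that the planned analysis says nothing about mediation. The documents do not support that. If an arm effect is first established, a non-significant arm term is more frequent under full mediation (about 95%) than under a wholly direct effect (66% or 40%), so it carries some information.

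A reader might also infer that the plan would usually miss true mediation, because requiring the arm effect to be significant first and then lost succeeds in only 2-15% of fully mediated trials at shifts of 0.2-0.5 SD. That rule is not in the protocol either, and the low figure mostly reflects low power for the total effect. At 0.5 SD and OR 3 per SD, the arm effect is significant in 17.8% of trials and then lost in 15.1%, that is 15.1/17.8 = 85% of the significant ones. Nor is it fair to set that figure against a joint test of the two paths, which asks whether there is any indirect effect, not whether mediation is complete.

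Hypothesising full mediation is not in itself a fault, since it is the working model of the power paragraph. The protocol also leaves the alcohol measure open (PEth is planned as a dichotomy, while the path models refer to levels) and does not pair alcohol visits with outcome visits. These are missing details, not errors.

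**Conclusion.** The point holds in a limited form. As written, the path analysis has one stated result, which without an established total effect does not show mediation, and an alcohol path with no stated adjustment for conditions that the protocol itself links to drinking and to PrEP behaviours.

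The size of the confounding problem depends on assumptions. False mediation is about 14-29% with a strong common cause at 0.3-0.5 SD and about 8% with a weaker one at 0.5 SD, against 2-4% after adjustment. With the weaker cause at 0.3 SD, the unadjusted rate is only about 4%. It would be wrong to infer that a mediation finding here would probably be spurious; the documents give no path strengths. The adjusted figures assume that the common cause is fully measured.

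The consequence is minor. No Specific Aim concerns mediation, the analysis is additional, and the feasibility results and mixed-model arm comparisons do not depend on it.

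**What to change.** In the Statistical analyses paragraph:

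1. Replace the hypothesis that the arm difference vanishes with an estimated indirect effect and bootstrap 95% CI.
2. Report the direct effect with its CI.
3. Adjust the alcohol-to-outcome path for baseline alcohol, CESD-10 and NIDA M-ASSIST. Where events are few, use penalised estimation. For suboptimal adherence at OR 1/3, about 0.30 × 40 + 0.125 × 80 = 22 events are expected.
4. Label the analysis exploratory.

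All these variables are already collected, so the cost is wording, some extra analysis, some power and a less definite causal statement. Power stays low: about 15% at a 0.2 SD shift and OR 2 per SD before the loss from covariates. In a simulation with a strong common cause, a 0.5 SD shift and OR 2 per SD, full mediation was detected in 37% of trials with four baseline covariates (the three above plus the baseline outcome, penalised) and in 49% with CESD-10 and M-ASSIST alone.

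The text should also state what adjustment leaves open. Baseline covariates do not remove confounding by follow-up depression or substance use, which the intervention's resource module may itself change.

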Individuals who indicate that they would like to participate will complete either a brief, self-administered tablet-based eligibility screener or an over-the-phone screener (see “Pre-Screening Questionnaire” attachment), and qualifying individuals will be offered participation and asked to provide informed written consent (see “Consent Form” attachment). Potential participants will be encouraged to take as much time as they need to review the information and only give consent when they are ready to participate. The study comprises of a baseline session, and two follow-up visits at 3- and 6- months post initial visit. Designated CAMH staff members will conduct and oversee all study procedures.

Pre-Screening

A CAMH research staff member will introduce the study to the potential participant using the pre-screening script (see “Pre-Screening Script” attachment). Individuals interested to take part in the study will complete an eligibility pre-screening questionnaire (see “Pre-Screening Questionnaire” attachment) Pre-screening will take approximately 5 minutes to complete and will be conducted over the phone or in person. Questions in the screener ask participants about their age, time on PrEP, sexual orientation, and alcohol consumption patterns.

Baseline Session

During their baseline session, participants will provide samples of dried blood spots (DBS) via finger prick (see “Dried Blood Spot Testing” below and “Dried Blood Spot” attachment) and complete a self-administered tablet-based survey. The survey, which is based on the previously-approved survey that was employed in the first phase of this project (CAMH REB# 101/2017; UHN REB#18-5014), will include measures assessing PrEP-related behaviors and other key factors including alcohol use, substance use, and depression (see “Measures” below and the “Survey” attachment). Upon completion of the survey, the tablet-based program will randomly assign participants to either the intervention condition or TAU based on a 2:1 intervention:TAU ratio. Intervention condition participants will receive a one-time, alcohol-focused brief behavioural personalized feedback intervention delivered seamlessly on the same tablet, which will also embed supplementary modules focused on substance use and depression when necessary (see “Intervention” below and the “Intervention” attachment).

Intervention

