The primary intervention component is The Check Your Drinking (CYD) intervention, a brief and personalized online intervention designed to assess and provide feedback on quantity and frequency of drinking, as well as the severity of hazardous drinking.²¹ CYD has been previously approved by CAMH REB [Protocol # 075/2016]. In the intervention, after completing the alcohol assessment, participants will be provided with a personalized drinking feedback report that compares their drinking with other Canadian males of the same age. This report also includes other relevant feedback, including an assessment of severity of alcohol use, and provides recommendations for safe levels of alcohol consumption. The development of the CYD was led by CAMH Senior Scientist [name] (Co-Investigator), and it has been subjected to five randomized trials from two independent research groups, all of which displayed a significant impact of the intervention to reduce hazardous alcohol consumption compared to controls.²¹⁻²⁵

An additional module will be appended to the CYD intervention and will appear for participants for whom a potential substance use- and/or depression-related issue is reflected in their self-reported survey responses. The module will be similar to components used in a previously validated, electronically-delivered ART adherence promotion intervention that the PI of the proposed research helped develop.²⁶ For the present trial, the module will include a list of local resources and support services for mental health and addictions concerns, along with contact information, web links, and other details for each of these entities. Participants in this arm only (intervention arm) can decide whether to include an email address of their choice if they would

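### The path model names alcohol as the only mediator, so a vanishing arm difference would not show that alcohol is the mechanism if depression or substance use moves with drinking

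*Combined protocol and SAP*

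**What the plan says.** The path analysis is described in one sentence at the end of Data Analysis, Statistical analyses. Its purpose is causal: "For the quantification of the causal impact of alcohol, we will additionally use path models". One variable is named ("where alcohol consumption levels will be introduced into the equations"), and the hypothesis is that "the introduction of this variable will make the differences between experimental and control groups disappear". No other mediator, covariate or sensitivity analysis is named for this model.

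Other sections describe a broader intervention and a broader causal picture:

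- II. Rationale and Study Objectives says the intervention will "distinctly target alcohol consumption and address key concurrent conditions among hazardous drinking, PrEP-prescribed MSM", and that these conditions may jointly harm PrEP-related behaviours.
- I. Introduction and Background says: "Substance use and depression frequently co-occur with alcohol consumption among MSM populations".
- Baseline Session describes the tablet intervention, "which will also embed supplementary modules focused on substance use and depression when necessary". Under Intervention, the extra module "will appear for participants for whom a potential substance use- and/or depression-related issue is reflected in their self-reported survey responses". The control arm gets neither the alcohol feedback nor the module.
- Additional Measures, on the NIDA M-ASSIST and the CESD-10, says: "Both measures will be administered at baseline and at the two follow-up time points". Statistical analyses gives these scores no role.

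**The concern.** A path model attributes the arm effect to alcohol through the association between follow-up drinking and the outcome within arms. Randomisation protects the arm comparison but not that association. If men who drink more at follow-up are also more depressed or use more drugs, and those conditions affect adherence, alcohol stands in for them when it is the only variable entered. The arm difference can then shrink on adding alcohol even if alcohol has no effect on the outcome.

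What is at stake is the trial's statement about mechanism. The Rationale expects the findings to guide later work on drinking and concurrent conditions in PrEP care. Crediting alcohol with an effect that belongs to a co-occurring condition would point that work at the wrong target.

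**Working it through.** **Inputs.** From the protocol: 120 men randomised 2:1, so 120 × 2/3 = 80 intervention and 40 control; alcohol as the only named mediator; depression and substance use scores at baseline, 3 and 6 months; 30% suboptimal adherence assumed in Statistical power. The protocol gives no path coefficient, correlation or power figure for this model, so there is nothing to reproduce. Every path value below is an assumption.

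**Model.** Let T be arm, A follow-up alcohol and D a follow-up depression or substance use score, in within-arm SD units:

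- A = aA·T + eA, D = aD·T + eD, corr(eA, eD) = rho
- Y = bA·A + bD·D + e

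The total arm effect is aA·bA + aD·bD. Alcohol's true indirect effect is aA·bA. With D left out, the model returns aA·(bA + bD·rho). The bias is therefore **aA·bD·rho**, and the remaining arm difference is bD·(aD − rho·aA).

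**No true alcohol effect (bA = 0).**

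| aA, aD, bD | Total | rho | Credited to alcohol | Share | Remaining |
|---|---|---|---|---|---|
| −0.4, −0.2, 0.4 | −0.080 | 0 | 0 | 0% | −0.080 |
| | | 0.3 | −0.048 | 60% | −0.032 |
| | | 0.5 | −0.080 | 100% | 0 |
| −0.3, −0.3, 0.3 | −0.090 | 0 | 0 | 0% | −0.090 |
| | | 0.3 | −0.027 | 30% | −0.063 |
| | | 0.5 | −0.045 | 50% | −0.045 |

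The true share is 0% in every row.

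**Module without effect (aD = 0).** aD is not in the bias formula. With aA = −0.4 and bD = 0.4, the false indirect effect is still −0.048 at rho = 0.3 and −0.080 at rho = 0.5.

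**Alcohol does act (bA = 0.3, aA = −0.4, bD = 0.4).** The truth is −0.4 × 0.3 = −0.120. The alcohol-only model gives −0.4 × (0.3 + 0.4 × 0.3) = −0.168 at rho = 0.3 (40% too large) and −0.4 × (0.3 + 0.4 × 0.5) = −0.200 at rho = 0.5 (67% too large).

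**Does baseline adjustment help?** Assume a baseline correlation of 0.5 and stability of 0.7, with bA = 0, aA = −0.4 and bD = 0.4. The follow-up correlation is 0.7² × 0.5 + (1 − 0.7²) × r, where r is the correlation of changes after baseline. Adjusting for both baselines leaves r.

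| r | Follow-up correlation | False effect, unadjusted | False effect, adjusted |
|---|---|---|---|
| 0 | 0.245 | −0.039 | 0 |
| 0.25 | 0.3725 | −0.060 | −0.040 |
| 0.5 | 0.50 | −0.080 | −0.080 |

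Simulation agrees (−0.040 to 0.000; −0.061 to −0.041; −0.079 unchanged). Adjustment works when the correlation comes only from stable traits. It does not when the conditions move together after baseline.

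**At this sample size.** In simulated trials of 80 v 40 with the first set of paths and bA = 0, the alcohol-to-outcome path reached significance in 22% (rho = 0.3) or 53% (rho = 0.5) of trials, against 5% with D in the model. With the second set and rho = 0.5 it was 34% against 4%. Entering D returned the true indirect effect within simulation error. These simulations contain no other confounder and no effect of alcohol on D.

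**The case against.** The defence has several good points.

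- *The extra module is slight.* It is a list of services shown only to flagged men. An average effect of 0.2 SD over all 80 men needs 0.2/0.5 = 0.4 SD among recipients if half are flagged, or 0.2/0.3 = 0.67 SD if 30% are. This stands: 0.2 SD may be generous. It does not rescue the model, because the bias does not depend on aD. It also means that the multi-target design is not the source of the problem. This is mediator-outcome confounding, which an alcohol-only intervention could show too.
- *Full disappearance is a product of the inputs.* This stands. The remaining difference is exactly zero only when aD = rho·aA, as in −0.2 = 0.5 × −0.4. With equal arm effects half of the difference remains at rho = 0.5.
- *There may be little to explain.* In the first scenario the arm effect of 0.08 reached p < 0.05 in about 7% of simulated trials. A reader might infer that the trial will report alcohol as the mechanism when it is not; the documents support only that it could.
- *Other variables are not excluded.* True. None is named, however, and the hypothesis is framed around one variable.
- *The joint model has its own limits.* If alcohol itself changes depression or drug use, the joint model removes that part of alcohol's effect. Suppose alcohol acts only through D, with a link of 0.3 per SD: its effect is −0.4 × 0.3 × 0.4 = −0.048, and the joint model's alcohol path gives 0. Additive mediators also do not test the synergy that the Rationale describes.
- *It is an additional analysis in a pilot.* True, and this limits the weight of the point.

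**Conclusion.** The concern holds in a conditional form. As written, the path model cannot separate alcohol's effect from that of conditions the protocol itself says co-occur with drinking and may harm PrEP-related behaviours. A vanishing arm difference is therefore not evidence that alcohol is the cause.

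The size depends on assumed paths and on the within-arm correlation, which the protocol does not give. With no true alcohol effect, the share wrongly credited runs from 0% at rho = 0 to between 50% and 100% at rho = 0.5 in the two settings shown. The sizes come from linear models and would differ for binary outcomes.

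Two stronger readings are not supported. One is that baseline adjustment cannot help: it can, when the correlation comes only from stable traits, and the protocol states only that the conditions co-occur. The other is that the trial's efficacy results are compromised: the arm comparisons for Aims 2 to 4 do not use this model and are unaffected.

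**What to change.** In Data Analysis, Statistical analyses:

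1. Specify a joint path model with follow-up alcohol, CESD-10 and NIDA M-ASSIST scores as mediators with correlated residuals, each adjusted for its baseline value.
2. Report alcohol's indirect effect from that model with a bootstrap interval, beside the alcohol-only model.
3. State that disappearance of the arm difference in the alcohol-only model will not be taken as evidence that alcohol is the cause.
4. State three limits: the joint estimate excludes any alcohol effect acting through depression or drug use; it still assumes no other unmeasured mediator-outcome confounding; and it does not test synergy.
5. Use continuous scores, including the four-week percentage of doses taken for adherence, and label the analysis exploratory.

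The cost is wording and a larger model, with no new data. In a linear model at rho = 0.5, the standard error of the alcohol path rises from about 0.10 to 0.11 (0.098 to 0.107). Binary adherence is the tighter constraint: 0.30 × 120 = 36 events against seven terms (arm, three mediators, three baselines) is about 5 events per parameter, which is the reason for item 5.
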